6.2 Recording of data

Web Based Data Capture (WBDC) will be used for data collection and query handling. The investigator will ensure that data are recorded on the CRFs as specified in the protocol and in accordance with the instructions provided.

The investigator ensures the accuracy, completeness, and timeliness of the data recorded and for the provision of answers to data queries according to the Clinical Study Agreement or applicable information. The investigator will sign the completed CRFs. A copy of the completed CRFs will be archived at the study site.

6.3 Screening procedures and baseline assessment

6.3.1 Enrollment and screening

At enrollment, each potential patient will provide informed consent prior to starting any study specific procedures. The screening procedures are summarized in Table 2 and Table 3.

Each potential patient is assigned a unique enrollment number. If a patient withdraws from the study, then the enrollment code cannot be reused.

A standard medical, medication and surgical history will be obtained with review of the selection criteria with the patient.

Each patient will undergo screening (Table 2 and Table 3) up to 28 days prior to first dosing to confirm eligibility. TB screening will be done using PPD test or chest X-ray/CT or following local practice. Tumor assessments and other clinical data obtained as standard of care prior to consent may be used for the study provided the assessments fall within the protocol specified period prior to the first dose of study drug.

All patients should have Brain MRI within 28 days of first dose to exclude CNS lymphoma.

Prior to discharge from each in-patient and clinic visit, the Investigator or their deputy will be responsible for reviewing all available data including vital signs and ECG tracings.

6.3.2 Patient demographics/Other baseline characteristics

Demographic data and other characteristics will be recorded and will include date of birth or age, gender, race and/or ethnicity according to local regulations.

The important findings of medical, medication and surgical history during eligibility review (i.e. previous diagnoses, disease, surgeries and current medication) will be collected and captured in the eCRF.

Disease background information will be collected, including:

- 1. Pathology (pathological subtype).
- 2. History of lymphoma and current disease status/staging (see Table 4).
- 3. Bone marrow involvement status.

- 4. History of prior anti-cancer treatment, i.e. chemotherapy(ies), HDAC inhibitor(s), CD30 targeting therapy(ies) for CD30+ subtypes, and ALK inhibitor(s) for ALCL-ALK+.
- 5. History of radiotherapy.
- 6. History of stem cell transplantation. The patients enrolled in this study should be transplant-ineligible, and their reasons for ineligibility should be collected, i.e. disease status (active disease), comorbidities or other factors.

Table 4 Revised Ann Arbor Staging System

Stage	Involvement	Extra-nodal (E) status
Limited		
I	One node or a group of adjacent nodes	Single extra-nodal lesions without nodal involvement
п	Two or more nodal groups on the same side of the diaphragm	Stage I or II by nodal extent with limited contiguous extra-nodal involvement
II bulky*	II as above with "bulky" disease	Not applicable
Advanced		
ш	Nodes on both sides of the diaphragm; nodes above the diaphragm with spleen involvement	Not applicable
IV	Additional noncontiguous extralymphatic involvement	Not applicable

Note: Extent of disease is determined by PET/CT for avid lymphomas and computed tomography for non-avid histology. Tonsils, Waldeyer's ring, and spleen are considered nodal tissue.

Whether stage II bulky disease is treated as limited or advanced disease may be determined by histology and a number of prognostic factors.

6.4 Safety procedures

6.4.1 Physical examination

A complete physical examination will be performed at the visits as indicated in the Study Plan (see Table 2 and Table 3). The assessment should include, but not limit to, the following body systems: general appearance, skin, lymph nodes, musculoskeletal/extremities, cardiovascular, lungs, abdomen, and neurological.

Performance status will be assessed at the visits as indicated in the Study Plan (see Table 2 and Table 3). The ECOG performance status below includes scales and criteria used to assess how a patient's disease is progressing and how the disease affects the daily living abilities of the patient, and to determine appropriate treatment and prognosis. Performance status will be assessed at screening, prior to first dose of each cycle, and at discontinuation according to ECOG criteria as follows:

0 = Fully active, able to carry out all pre-disease activities without restrictions.

- 1 = Restricted in physically strenuous activity but ambulatory and able to carry out work of a light or sedentary nature e.g., light housework, office work.
- 2 = Ambulatory and capable of self-care, but unable to carry out any work activities. Up and about more than 50% of waking hours.
- 3 = Capable of only limited self-care, confined to bed or chair more than 50% of waking hours.
- 4 = Completely disabled, cannot carry on self-care, totally confined to bed or chair.

6.4.2 Vital signs

Supine blood pressure and pulse rate

Supine blood pressure and pulse rate will be measured after 10 minutes rest. Assessments will be performed at the visits as shown in the Study Plan (see Table 2 and Table 3). Observations will be recorded at the following times:

> Part A Dose escalation and extension cohorts

- Screening.
- First day of multiple dosing (Day 1 Cycle 1): pre-dose and 1, 2, 4, 8, 24 hours post first dose.
- Presumed steady state (Day 8 and Day 15 of Cycle 1): pre-dose.
- Presumed steady state (Day 1 Cycle 2): pre-dose, 1, 2, 4, 8 hours post dose.
- On Day 1 of each subsequent Cycle: one assessment at any time during day.
- On occurrence of any cardiac AE.
- Discontinuation visit.

Part B Dose expansion cohort

- Screening.
- First day of multiple dosing (Day 1 Cycle 1): pre-dose and 1, 2, 4, 8 hours post first dose.
- Presumed steady state (Day 8 and Day 15 of Cycle 1): pre-dose.
- Presumed steady state (Day 1 Cycle 2): pre-dose, 1, 2, 4, 8 hours post dose.
- On Day 1 of each subsequent Cycle: one assessment at any time during day.
- On occurrence of any cardiac AE.
- Discontinuation visit.

Time points of measurement may be adjusted on the basis of emerging PK and safety data. Patients with dose interruption do not require multiple monitoring of vital signs during the period of the dose interruption.

Body temperature

Body temperature will be measured in degrees Celsius at the screening and then Day 1 of each cycle, and at the discontinuation visit, as indicated in the Study Plan (Table 2 and Table 3).

Weight

Weight will be performed at screening and then Day 1 of each cycle and at the discontinuation visit.

Height

Height will be assessed at screening only.

Vital signs should be assessed additionally at the discretion of the Investigator if clinically indicated. There is a +/- 15-minute window for the collection of vital signs performed at pre-dose and 1-10 h, and a 1-hour window for vital sign assessment performed at 24 h. The timing and frequency of vital sign assessment may be adjusted in response to the emerging PK and safety profile. Any changes in vital signs should be recorded as an AE if applicable.

6.4.3 ECG

Resting 12-lead ECG

Twelve - lead triplicate ECG will be performed at the visits as shown in Study Plan (Table 2 and Table 3) at the following time points:

> Part A Dose escalation and extension cohorts

- Screening.
- First day of multiple dosing (Day 1 Cycle 1): pre-dose, 1, 2, 4, 8 and 24 hours post dose.
- Presumed steady state (Day 8 and Day 15 of Cycle 1): pre-dose.
- Presumed steady state (Day 1 Cycle 2): pre-dose, 1, 2, 4, 8 hours post dose.
- Day 1 Cycle 3 and Day 1 Cycle 4: pre-dose.
- On Day 1 of each subsequent Cycle: one assessment at any time during day.
- On occurrence of any cardiac AE.
- Discontinuation visit.

> Part B Dose expansion cohort

- Screening.
- First day of multiple dosing (Day 1 Cycle 1): pre-dose, 1, 2, 4 and 8 hours post dose.
- Presumed steady state (Day 8 and Day 15 of Cycle 1): pre-dose.
- Presumed steady state (Day 1 Cycle 2): pre-dose, 1, 2, 4, 8 hours post dose.

- On Day 1 of each subsequent Cycle: one assessment at any time during day (except predose on Day 1 of Cycle 4 and 6).
- On occurrence of any cardiac AE.
- Discontinuation visit.

The timing and number of ECGs may be adjusted in response to the emerging PK and safety data. Patients with dose interruption do not require multiple monitoring of ECG during the period of the dose interruption.

Twelve-lead ECGs will be obtained after the patient has been resting semi-supine/supine for at least 10 minutes prior to each time point indicated. All ECGs should be recorded with the patient in the same physical position. For each time point, all three ECGs should be taken at about 5-minute intervals, and the triplicate ECGs should be done within 15 minutes before corresponding PK sampling, including pre-dose and 1 - 8 h post-dose. As for 24 h post-dose ECGs, all three recordings should be performed within 1 hour before corresponding PK sampling.

A standardised ECG machine should be used and the patient should be examined using the same machine throughout the study, where feasible.

After paper ECGs have been recorded, the investigator or designated physician will review each of the ECGs and may refer to a local cardiologist if appropriate. A paper copy should be filed in the patient's medical records. If an abnormal ECG finding at screening or baseline is considered to be clinically significant by the investigator, it should be reported as a concurrent medical history condition. If there is a clinically significant abnormal ECG findings during the treatment period, this should be recorded on the AE CRF, according to standard adverse events collection and reporting processes (see section 6.5.3 and 6.5.4). It is recommended that asymptomatic ECG findings should be adjudicated by an expert reader in case they are reported as AEs with the ECG abnormaity given as explantory information. For all ECGs details of rhythm, PR, R-R, QRS and QT intervals and an overall evaluation will be recorded. All ECGs of patients with any value > 470 ms QTcF are to be sent for immediated review by the study team.

All ECG data will also be collected digitally for each patient and will be transferred electronically for central analysis as described in the study specific ECG manual (if applicable). Heart rate, PR, R-R, QRS and QT intervals will be determined and reviewed by an external cardiologist (if applicable).

Confirmed QTc prolongation (> 500 msec absolute or > 60 msec above baseline) is the dose interruption criteria.

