Subjects who are discontinued from study drug for any reason (i.e., AE or administrative reasons etc.) other than disease progression should not be considered withdrawn from the study. They will continue to be followed for efficacy evaluations per schedule outlined in Table 3 until subject exhibits first progression, withdrawal of consent, death, lost to follow-up, or study termination from sponsor, whichever occurs first. If subjects refuse to return for these visits or are unable to do so, every effort should be made to contact them or obtain information by telephone to determine the subject's disease status and survival.

Figure 2 Schema for dose expansion study (Part B)

Abbreviations: PTCL, peripheral T cell lymphoma; PO orally taken; EOT, end of treatment; PD, progressive disease

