5.1.3 Dose modifications

5.1.3.1 Toxicity management and dose modifications to AZD4205

If a patient has a treatment emergent adverse event (TEAE) at least possibly related to AZD4205, then dose interruptions/holds with possible modifications as described in Table 1 should be implemented. Deviations from these guidelines may occur based on the clinical judgment of the investigator with notification to the Sponsor. For managing toxicity related to the eye, refer Appendix VII.

Table 1 Dose Interruptions/Modifications for Toxicities Observed in the Study

Category	Toxicities needing immediate interruption	Dose modification plan
	$\mathrm{ANC} < 0.5 \times 10^9/\mathrm{L}$	Immediate interruption of AZD4205. Once toxicity has resolved to recovery to ≤ Grade 2 or baseline within 14 days of onset: Resume at the same dose for the 1st occurrence of the event Resume at the reduced dose for the 2nd occurrence of the event Permanent discontinue for the 3rd occurrence of the event
Hematological	Platelet count $< 25 \times 10^9/L$	Immediate interruption of AZD4205 Once toxicity has resolved to recovery to ≤ Grade 2 or baseline within 21 days of onset: Resume at the same dose for the 1st occurrence of the event Resume at the reduced dose for the 2nd occurrence of the event Permanent discontinue for the 3rd occurrence of the event
toxicity	Grade 3 febrile neutropenia	Immediate interruption of AZD4205 Once toxicity has resolved to recovery to ≤ Grade 2 or baseline within 14 days of onset: Resume at the reduced dose for the 1st occurrence of the event, unless the toxicity can be safely and reliably controlled to ≤ Grade 2 or baseline with appropriate treatment, (dose may restart at 150 mg once daily after reaching an agreement with the sponsor). If the same non-hematological toxicity requiring dose interruption occurs again, AZD4205 should be permanently discontinued.
	Grade 3 thrombocytopenia with significant bleeding Other Grade 4 or unmanageable hematological toxicity(ies)	Permanent discontinuation Immediate interruption of AZD4205

		Once toxicity has resolved to recovery to \leq Grade 2 or baseline within 14 days of onset:
		Resume at the same dose for the 1st occurrence of the event
		 Resume at the reduced dose for the 2nd occurrence of the event
		 Permanent discontinue for the 3rd occurrence of the event
	QTcF > 500 ms absolute or > 60 ms increase from baseline	Permanent discontinuation

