5.2.2 Potential risks

Non-clinical toxicity studies of AZD4205 in rats and dogs and safety pharmacology experiments have been summarized in Section 2.3 of this protocol, which may indicate the potential adverse effects of AZD4205 in human. Further detailed information of non-clinical toxicity findings is available in the Investigator Brochure. The monitoring and management of the potential adverse effects of using AZD4205 is discussed below.

Cardiovascular effects

Patients who have unstable cardiac conditions and risk factors for QT prolongations will be excluded from participation in this study (detailed exclusion criteria are listed in Section 4.2). Concomitant use of regular medications that may prolong the QT interval will be restricted whenever feasible (See Appendix II), but patients may receive any medication that is clinically indicated for the treatment of AEs. Electrolyte and vital sign assessments, including pulse rate and blood pressure, will be monitored regularly throughout the study (See Section 6.1). Twelve lead ECG will be conducted throughout the study to monitor any

change of QT interval. Confirmed QTc prolongation (> 500 msec absolute or > 60 msec above baseline) is the dose interruption criteria (See Section 6.4.3). The investigator or designated physician will review each ECG prior to discharge from the clinic and may refer to a local cardiologist if appropriate for immediate management of the patients. A paper copy should be filed in the patient's medical records. If an abnormal ECG finding at screening or baseline is considered to be clinically significant by the investigator, it should be reported as a concurrent condition. An Echocardiogram or MUGA scan to assess LVEF will be performed at screening prior to first dose of AZD4205 to evaluate any pre-existing cardiac abnormality, followed by Cycle 3 Day 1, and then every 12 weeks, and wherever and whenever necessary as clinically indicated throughout the study. An asymptomatic LVEF decrease to < 40% or LVEF [40-54%] and LVEF decrease ≥ 10% from baseline or any symptomatic LVEF decrease are the dose interruption criteria (See Section 6.4.5 and Appendix VII). Both high sensitive troponin T testing and NT-pro BNP will be performed at screening, baseline and each subsequent cycle.

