5.3.1 Procedures for discontinuation of a patient from investigational product

Patients may be discontinued from investigational product in the following situations:

- Patient decision. The patient is at any time free to withdraw his/her participation in the study, without prejudice.
- Adverse events (see Table 1).
- Initiation of further line(s) of anti-cancer treatment (including bone marrow transplantation).
- Severe non-compliance to this protocol as judged by the investigator and/or Study Team.
- Disease progression as per 2014 Lugano classification, unless, in the opinion of the investigator, the patient is still deriving clinical benefit.
- Patients incorrectly initiated on investigational product (Section 5.3.2).
- Patient achieved a satisfying response confirmed for 1 year by PET or CT assessment (Section 5.1.4).
- Treatment duration reaching 2 years (approximately 35 cycles) (Section 5.1.4).

• Pregnancy.

Once study medication is permanently discontinued it cannot be restarted.

Any patient who discontinues study treatment for reasons other than disease progression should have response assessment performed as scheduled in the protocol until disease progression is documented or death occurs, unless consent is withdrawn. Study procedure related SAEs and anti-cancer treatment must be captured until the patient no longer has response assessments (disease progression or permanent withdrawal from the study).

After the final database lock, there may be some patients remaining on study treatment. For these patients, sponsor will collect information during the treatment period and for 28 days (\pm 7 days) after last dose on SAEs, death (including those due to disease progression), discontinuation due to AEs/SAEs and drug accountability.

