- and symptoms associated with the abnormal finding should be reported as the AE with the ECG abnormality given as explanatory information.
- Management of QTc prolongation: A QTcF > 500 ms is an independent criterion for individual pro-arrhythmic risk. Any QTcF > 500 ms should trigger a repeat ECG timepoint in 5-10 min to confirm the finding. If confirmed, patient will be withdrawn from study Patients experiencing QTc interval prolongation with signs/symptoms of serious arrhythmia will not be permitted to restart study treatment.

Safety monitoring with Echocardiogram/MuGA:

- The modality of the cardiac function assessments must be consistent within a patient i.e. if echocardiogram is used for the screening assessment then echocardiogram should also be used for subsequent scans.
- The patients should also be examined using the same machine and operator whenever
 possible, and quantitative measurements should be taken. Recommendations include having
 complete high quality standardized 2-D with Doppler echocardiographic examinations
 performed by an experienced sonographer and include evaluation of both systolic and
 diastolic left ventricular function.
- Ejection fraction determinations should be determined quantitatively based on bi-plane measurements of end diastolic and end systolic left ventricular volumes.
- Any symptomatic decrease in LVEF will prompt the discontinuation of the treatment and a cardiac consultation.
- Below table is the reference for the management of asymptomatic decrease of LVEF:

Absolute EF	Decrease from Baseline <10%	Decrease from Baseline 10-15%	Decrease from Baseline >15%
55% or above	Continue	Continue	Interruption*. ECHO/MUGA in 3 weeks. If value back to baseline, consider dose resumption.
54-40%	Continue	Interruption. Cardiac consultation. ECHO/MuGA in 3 weeks. If LVEF above 55% consider dose resumption	Discontinue. Cardiac consultation
Below 40%	Interruption. Cardiac consultation	Discontinue. Cardiac consultation	Discontinue. Cardiac consultation

Footnote: *A subject with EF decreasing by > 15% and remaining > 55% would have to start from > 70%, i.e. a very high normal. Hypovolemia, hyperthyroidism and hypertrophic/constrictive/significant restrictive cardiomyopathy should be considered and ruled out.

Troponin and NT-pro BNP

- Both high sensitivity troponin T testing (TnT or hs-TnT) and NT-pro BNP will be performed.

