2.1.1 Primary Objective, Endpoint and Estimand

Primary Objective	Endpoint/Variable

To assess the anti-tumor efficacy of AZD4205 using CT-based objective response rate (ORR) as primary efficacy endpoint in patients with r/r PTCL	
CT-based ORR evaluated by independent review committee (IRC), according to 2014 Lugano classification

Estimand of primary objective

Treatment: Participants will receive AZD4205 capsule.

Population: Patients with relapsed or refractory peripheral T-cell lymphoma (PTCL). Evaluable for CT-based response set will be used for analysis, including all dosed central pathology confirmed PTCL participants with baseline measurable disease confirmed by IRC using CT imaging.

Statistical Analysis Plan of PTCL (Version 3.0)

Protocol Code: DZ2019J0005 (Part B)

Date: Mar 25, 2023

Variable (or endpoint): Binary variable indicating whether a participant is a responder who achieved complete response (CR) or partial response (PR), evaluated by IRC based on CT imaging according to Lugano criteria.

Intercurrent Events and strategies:

Intercurrent Events	Strategies for ORR
Discontinuation of study treatment due to reasons other than progressive disease (PD)	Treatment policy: Occurrence of intercurrent event ignored.
PD	While on treatment: The intercurrent event is already captured in the variable definition.
New anti-cancer therapy	While on treatment: Response to treatment prior to the occurrence of the intercurrent event is of interest.

Population-level summary: CT-based ORR assessed by IRC according to Lugano.

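### One QTc finding leads to dose interruption, permanent discontinuation or study withdrawal depending on the protocol section, and study withdrawal conflicts with the planned efficacy follow-up

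*Protocol*

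**What the plan says.** Four places in the protocol attach an action to QTc prolongation during treatment.

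- Section 6.4.3 (ECG): "Confirmed QTc prolongation (> 500 msec absolute or > 60 msec above baseline) is the dose interruption criteria". Section 5.2.2 (Potential risks) repeats the rule and refers the reader to 6.4.3.
- Section 5.1.3.1, Table 1, has a row for "QTcF > 500 ms absolute or > 60 ms increase from baseline". The plan in that row is permanent discontinuation, with no resumption step and no mention of confirmation.
- Appendix VII, part 2 (Cardiovascular Effects): "Any QTcF > 500 ms should trigger a repeat ECG timepoint in 5-10 min to confirm the finding". It then says: "If confirmed, patient will be withdrawn from study".

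On follow-up after stopping drug, Section 3.1.3 says that Part B subjects taken off drug for any reason "other than disease progression should not be considered withdrawn from the study". Section 5.3.1 says that such a patient "should have response assessment performed as scheduled in the protocol until disease progression is documented or death occurs, unless consent is withdrawn". For ORR, SAP Section 2.1.1 handles treatment discontinuation without progression as "Treatment policy: Occurrence of intercurrent event ignored".

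**The concern.** A site that sees a confirmed QTcF above 500 ms can follow the protocol to the letter and hold the drug, stop it for good, or take the patient out of the study. These are not degrees of one action: Section 5.3.1 says that drug once permanently discontinued cannot be restarted, and Section 5.3.3 describes withdrawal from the study as covering both the product and the assessments.

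The rule concerns a known safety question. Section 2.3.2 reports QTc increases in dogs at every single dose tested (30, 60 and 100 mg/kg; 13 ms, or 6%, at 100 mg/kg) and again in the 1-month dog study. Section 5.1.1.1 lists the same QTc thresholds among the DLT-like events. Every dosed patient has repeated triplicate ECGs.

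The second stake is efficacy data. If Appendix VII is followed, scans stop for a patient whom the primary estimand, PFS and DoR all expect to be followed after drug is stopped.

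**Working it through.** The protocol states no figure for this point, so the check is mainly a comparison of texts.

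**Step 1. The four rules side by side.**

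| Place in protocol | Trigger | Confirmation | Action |
|---|---|---|---|
| 5.2.2 | QTc > 500 ms, or > 60 ms above baseline | Required, method not given | Dose interruption (refers to 6.4.3) |
| 6.4.3 | Same | Required, method not given | Dose interruption |
| 5.1.3.1, Table 1 | Same limits, as QTcF | Not mentioned | Permanent discontinuation |
| Appendix VII, part 2 | QTcF > 500 ms only | Repeat ECG after 5–10 min | Withdrawal from the study |

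Counting distinct actions by finding:

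- Confirmed QTcF > 500 ms: interruption, permanent discontinuation, study withdrawal. Three.
- Rise > 60 ms without exceeding 500 ms: interruption, permanent discontinuation. Two, because Appendix VII is silent.

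**Step 2. What study withdrawal does to follow-up.**

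- Protocol 3.1.3 and 6.9.1 run CT scans until progression or withdrawal from the study. Withdrawal under Appendix VII therefore ends scheduled scans.
- Protocol 3.1.3, 5.1.4, 5.3, 5.3.1 and 6.9.1 require response assessments to continue when drug is stopped for a reason other than progression.
- SAP 4.1.2.3, Table 1, row 5 uses data collected after treatment discontinuation when dating progression. Row 4 censors a patient who leaves the study without progression at the last adequate assessment. Appendix VII moves a patient from row 5 to row 4.
- SAP 4.1.2.1 gives DoR the PFS censoring time, so DoR moves with it.
- SAP 4.1.1 classes a patient with no post-baseline assessment as a non-responder.

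**Step 3. Timing.** In Part B, ECGs fall on Cycle 1 Days 1, 8 and 15 and Cycle 2 Day 1. The first scheduled CT is at Cycle 3 Day 1, which is study day 2 × 21 + 1 = 43, with a 7-day window. All four ECG visits, including both days with multiple time points, come before it. A patient withdrawn at one of them has no scheduled post-baseline scan and counts as a non-responder.

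**Step 4. Sensitivity of the primary test to one patient.** Inputs from Protocol 7.2 and SAP 2.4: n = 100, null ORR 15%, assumed ORR 27%, exact binomial test, two-sided 5% (2.5% in the upper tail).

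- P(X ≥ 22 | 0.15) = 0.0393, above 0.025.
- P(X ≥ 23 | 0.15) = 0.0221, below 0.025. The boundary is 23 responders.
- P(X ≥ 23 | 0.27) = 0.8448, which reproduces the stated 84.5% power.
- One responder is 1/100 = 1 percentage point of ORR.

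Step 4 shows only how little slack there is at the boundary. It does not estimate how many patients the QTc rules would affect.

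**The case against.** Several points can be made for the protocol.

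- *Interruption may be the trigger and discontinuation the consequence.* The Table 1 column holding this row is headed as toxicities that need immediate interruption, and Section 6.4.5 uses interruption criterion loosely for a symptomatic LVEF fall that then leads to discontinuation. This softens the first conflict but does not remove it. Section 5.2.2 points to 6.4.3, neither points to Table 1, and the Table 1 row has no resumption step where other rows spell one out.
- *The scope differs.* Table 1 applies to events at least possibly related to drug and allows deviation on clinical judgment. That is so, and it adds a further difference to reconcile: 6.4.3 and Appendix VII state no relatedness condition.
- *Withdrawn from the study may be loose wording for stopping drug.* The next sentence in Appendix VII is about restarting treatment, and many sections require continued assessment. The intent may well have been that. As written, though, Section 5.3.3 gives study withdrawal a meaning that includes assessments. The next sentence, which bars restart only for patients with signs of serious arrhythmia, also fits poorly with withdrawing every confirmed case.
- *There are safeguards.* Screening QTcF above 450 ms is an exclusion (Section 4.2), and ECGs of patients with any QTcF above 470 ms go to the study team at once (Section 6.4.3). This limits uneven handling, but the team still has no single written rule to apply.
- *The efficacy effect is unquantified.* This stands. ORR changes only if a first response would have come after drug was stopped and before new therapy. The primary set is also a subset of dosed patients, so n = 100 is the planning figure.

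**Conclusion.** The concern holds. For a confirmed QTcF above 500 ms the protocol prescribes three incompatible actions; for a rise above 60 ms alone it prescribes two. Confirmation is required in three of the four places, and only Appendix VII says how to obtain it. This must be fixed on patient-safety grounds alone.

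The efficacy consequence is real but secondary. Read literally, Appendix VII ends assessments that the protocol elsewhere requires and that the SAP relies on for ORR, PFS and DoR. Its size is unknown because the documents give no QTc event rate, and it may be small. The 22 versus 23 boundary assumes 100 evaluable patients. This assessment takes no position on which clinical action is right.

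**What to change.** Reconcile Protocol Table 1 (Section 5.1.3.1), Section 5.2.2, Section 6.4.3 and Appendix VII so that all four give the same thresholds, the same requirement and method for confirmation, the same relatedness condition and the same action for each limb, or have three of them refer to one governing text. The content of the rule is the sponsor's clinical decision.

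Separately, reconcile the withdrawal wording in Appendix VII with Sections 3.1.3, 5.3.1 and 5.3.3, so that stopping drug is distinct from ending response assessments and the data needed under the SAP's treatment-policy strategy and SAP Table 1, row 5, continue to be collected.

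The cost is wording at the next protocol amendment and a notice to sites. No procedures are added.
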